8.1. Efficacy Variables

Primary endpoint:

- Proportion of subjects exhibiting complete clearance of all treatable warts (baseline and new) at the Study Day 84 EOT Visit.

Secondary endpoints:

- Proportion of subjects exhibiting complete clearance of all treatable warts (baseline and new) at Visit 2, Visit 3, Visit 4, Follow-up Day 112, and Follow-up Day 147 EOS.

- Proportion of subjects exhibiting 90% and 75% clearance of all treatable warts (baseline and new) at Visit 2, Visit 3, Visit 4, Study Day 84 EOT, Follow-up Day 112, and Follow-up Day 147 EOS.
- Change from baseline in the number of treatable warts (baseline and new) at Visit 2, Visit 3, Visit 4, Study Day 84 EOT, Follow-up Day 112, and Follow-up Day 147 EOS.
- Change from baseline in the percent of treatable warts (baseline and new) at Visit 2, Visit 3, Visit 4, Study Day 84 EOT, Follow-up Day 112, and Follow-up Day 147 EOS.

Exploratory endpoints:

- Proportion of subjects exhibiting reduction of at least 1 treatable wart from baseline at Visit 2, Visit 3, Visit 4, Study Day 84 EOT, Follow-up Day 112, and Follow-up Day 147 EOS.
- Proportion of subjects who are clear at the Study Day 84 EOT Visit and remain clear at the Follow-up Day 112 and 147 EOS Visits.
- Change from baseline in total wart area (sum of individual warts) at Study Day 84 EOT, Follow-up Day 112 and Follow-up Day 147 EOS.
- Change from baseline in the percent of total wart area (sum of individual warts) at Study Day 84 EOT, Follow-up Day 112, and Follow-up Day 147 EOS.

8.2. Baseline Values

Unless otherwise noted, baseline is defined as the last non-missing value recorded prior to the first application of study drug. When applicable, unscheduled visits will be used in the determination of baseline values.

8.3. Adjustments for Covariates

Adjustments for gender and baseline values will be made for statistical analyses.

8.4. Handling of Dropouts or Missing Data

All subjects who were randomized will be evaluated in the ITT population. If a subject requests to be removed from the study due to study related adverse events or additional spreading of disease, data will be collected and analyzed as a treatment failure and not replaced. If a subject discontinues use of study drug but remains in the study, the subject will be analyzed as a non-responder as well. Per the study protocol, subjects who achieve complete clearance of all lesions prior to Day 84 are required to attend all Treatment Visits but will not receive treatment at those visits where all lesions are clear. These subjects will not be considered as having prematurely discontinued use of the study drug.

Unless described otherwise in subsequent sections, analyses will be carried out with the data available using no imputation for missing data. A description of how missing data will be handled for select endpoints is included below.

8.4.1. Coronavirus 19

Due to the coronavirus 19 (COVID-19) outbreak during the course of the study, there may be several subjects who will have missing assessments which could affect the primary analysis. Subjects who are unable to attend a study visit due to COVID-19 will be documented in the protocol deviation log. The protocol deviation date will be used as the COVID-19 affected date (or visit). If a subject reports an adverse event of COVID-19, then the event start date will be used as the affected date. In the event that a subject has an affected COVID-19 date from both sources, the earlier of the dates will be used.

Subjects who were affected by COVID-19 will be summarized in a data listing. The listing will contain the following information: subject number, treatment, gender, age, first date affected by COVID-19, duration in study prior to the affected COVID-19 date, total study duration, exposure to study drug, any COVID-19 related adverse events, completion/discontinuation of the study, and reasons for discontinuation. All data listings will include a flag to denote whether the subject and/or visit was affected by COVID-19.

8.4.2. Handling of Missing Data for Complete Clearance Endpoint

The efficacy endpoint, proportion of subjects exhibiting complete clearance of all treatable warts, is to be assessed (blinded assessment only) at Treatment Visits 2, 3, 4, Study Day 84 EOT visit, and Follow-up visits Day 112 and 147.

For the primary efficacy analysis, subjects who do not have an assessment of complete clearance of all treatable warts at any of the scheduled assessments (with applicable visit windows applied) will be considered to have not achieved complete clearance of all treatable warts at that visit.

Due to COVID-19, sensitivity analyses will be performed to assess the robustness of the primary analysis. The purpose of these analyses is to assess any potential bias due to subject assessments or missing data due to COVID-19. There will be two sensitivity analyses on the primary efficacy endpoint, complete clearance at Day 84.

- Exclude COVID-19 affected data: The first analysis will be to conduct the planned analysis only on the subjects who were not affected by COVID-19 at or before Day 84 (with visit window), i.e., if a subject was affected by COVID-19, then the subject will be removed from the analysis.
- Multiple imputation of missing data: The second analysis will be to use the multiple imputation regression method. For monotone missing data patterns, data in each treatment group will be imputed using the regression method on the basis of the predicted future pattern for the same treatment group. One hundred imputed

datasets will be generated. Each imputed dataset is analyzed separately using the method for the efficacy endpoint described in 9.1. The final estimate of treatment difference will be the average of the estimates based on the 100 individual imputed datasets. The pooling of the individual estimates and inferences based on the combined estimate will be handled by the SAS procedure MIANALYZE.

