12.7 Handling of Missing, Unused, and Spurious Data

Subjects who do not have an assessment of complete clearance of all treatable warts at the EOS visit (Study Day 84) will be considered to have missing data for the primary endpoint. The primary method to handle missing data will be to assign all subjects with missing complete clearance data as not having achieved complete clearance.

In the event a subject requests to be removed from the study due to study-related adverse experiences or additional spreading of disease, data will be collected and analyzed as a treatment failure and the subject may be replaced. Further discussion of how treatment failure will be utilized in analysis will be provided in the Statistical Analysis Plan.

The procedures for handling missing data for other study endpoints will be described in the Statistical Analysis Plan.

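### The COVID-19 multiple-imputation check is not limited to COVID-19 missingness, so a difference from the primary Day 84 result cannot be attributed to COVID-19

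*SAP*

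**What the plan says.** **Primary rule.** SAP 8.4.2 states that a subject without an assessment at a scheduled visit, after visit windows are applied, "will be considered to have not achieved complete clearance of all treatable warts at that visit". Protocol 12.7 has the same rule for Day 84: "The primary method to handle missing data will be to assign all subjects with missing complete clearance data as not having achieved complete clearance". Neither depends on why the value is missing.

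**Purpose of the two sensitivity analyses.** SAP 8.4.2 introduces them as a response to COVID-19: "The purpose of these analyses is to assess any potential bias due to subject assessments or missing data due to COVID-19".

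**First analysis.** It repeats the planned analysis without subjects affected by COVID-19 at or before Day 84. It is tied to COVID-19 status.

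**Second analysis.** "Multiple imputation of missing data: The second analysis will be to use the multiple imputation regression method". The description continues: "For monotone missing data patterns, data in each treatment group will be imputed using the regression method". There are 100 datasets, each analysed as in SAP 9.1 and then pooled. The bullet names no reason for missingness and makes no use of COVID-19 status.

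**Fixed failures.** SAP 8.4 covers subjects who ask to leave because of study-related adverse events or spreading disease: "data will be collected and analyzed as a treatment failure and not replaced". Subjects who stop study drug but stay in the study are also non-responders. SAP 8.4.2 does not say whether these rules hold inside the imputation.

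**COVID-19 information.** SAP 8.4.1 logs visits missed because of COVID-19 and dates each affected subject by the earlier of the deviation date and the start of a COVID-19 adverse event. It adds: "All data listings will include a flag to denote whether the subject and/or visit was affected by COVID-19".

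**The concern.** A check on COVID-19 missingness should return the primary result when no value is missing because of COVID-19. This one need not. It changes the rule for every missing Day 84 value at once, so two things vary together: how COVID-19 losses are treated and how ordinary losses are treated.

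Several ordinary losses fall outside the failure rules of SAP 8.4: loss to follow-up, withdrawal of consent for other reasons, withdrawal for noncompliance (Protocol 7.4.3), discontinuation for an adverse event on the judgment of the investigator, sponsor or medical monitor rather than at the subject's request (Protocol 7.4.1), and a Day 84 visit outside the SAP window of Days 74 to 94. Under the primary rule all of these are not clear. Under the imputation they become possible responders.

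At stake is the interpretation of the robustness statement. If the imputed and primary results differ, the report could name COVID-19 as the cause when ordinary dropout produced the gap.

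**Working it through.** The plan states no figure for this point, so there is none to reproduce. The check sets COVID-19 missingness to zero and asks whether the two analyses agree.

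**Arm sizes (from the documents).** Part B has about 90 subjects at 3:2:3:2, so 90 × 3/10 = 27 on VP-102 and 90 × 2/10 = 18 on placebo per regimen. Part A adds 5 and 1 for a selected regimen (5:1 in a group of 6). Pooled: 32 v 19.

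**Assumptions (not in the documents).** Clearance among those assessed is pT on VP-102 and pP on placebo. The non-COVID missing fractions are mT and mP. The imputation is approximated by each arm's observed clearance rate. A regression imputation would normally also use earlier visits, so the actual gap could be smaller or larger.

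**Formulas.**
- Primary difference: pT(1 − mT) − pP(1 − mP)
- Imputed difference: about pT − pP
- Gap: pT·mT − pP·mP

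**Results at 35% v 5% clearance, no COVID-19 missingness.**

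| Missing, VP-102 / placebo | Primary | Imputed | Gap |
|---|---|---|---|
| 0% / 0% | 30.0 | 30.0 | 0.0 |
| 10% / 10% | 27.0 | 30.0 | 3.0 |
| 20% / 20% | 24.0 | 30.0 | 6.0 |
| 20% / 10% | 23.5 | 30.0 | 6.5 |
| 10% / 20% | 27.5 | 30.0 | 2.5 |

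Values are percentage points. One VP-102 subject is 1/32 = 3.1 points, so 3 to 6 points is about one to two subjects. At 35% v 10% the gaps for equal missingness of 10% and 20% are 2.5 and 5.0 points; at 50% v 10% they are 4.0 and 8.0.

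**Worked example at 32 v 19.** VP-102: 9 clear, 6 missing. Placebo: 1 clear, 4 missing. None is due to COVID-19. Primary: 9/32 − 1/19 = 28.1% − 5.3% = 22.9 points. Imputation by random draws from each arm's observed rate, pooled by Rubin's rules, gives 27.5 points. The test statistic hardly moves (z 2.42 v 2.39, unstratified), because imputation also adds variance.

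**Keeping the SAP 8.4 failures.** At 35% v 5% with 20% missing in both arms, suppose half of the missing subjects are fixed as failures. The imputed difference is (0.35 − 0.05) × (0.80 + 0.10) = 27.0 points, so the gap falls from 6.0 to 3.0. It reaches zero only if every missing subject is fixed as a failure.

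**Excess dropout on VP-102.** Let clearance with missing = not clear be 30% in both arms, with dropout of 25% v 5%. Observed rates are 0.30/0.75 = 40.0% and 0.30/0.95 = 31.6%. Imputing everyone shifts the difference by 8.4 points. If the 20-point excess on VP-102 is scored as failure and only the balanced 5% is imputed, the arms are 0.30 + 0.05 × 0.400 = 32.0% and 0.30 + 0.05 × 0.316 = 31.6%, a shift of 0.4 points.

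**After the proposed change.** With no COVID-19 missingness nothing is imputed, so the gap is exactly 0.

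**The case against.** The strongest reply has four parts.

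1. **The bullet can be read in context.** The sentences before it speak of missing data due to COVID-19, and the bullet may refer back to that. This is possible, but nothing in the bullet says so, whereas the first bullet states its restriction. A programmer following the text would impute every missing value. The reply supports a clarification rather than removing the need for one.

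2. **Tolerability withdrawals are already handled.** VP-102 is a blistering agent, so a reader might infer that the imputation turns excess VP-102 withdrawals into responders and favours the less tolerable regimen. The documents do not support that. SAP 8.4 scores withdrawal at the subject's request for study-related adverse events or spreading disease as failure, and the last calculation above shows the shift falling from 8.4 to 0.4 points when that rule holds. No dropout rate is given, and higher placebo dropout would push the other way. This part stands, except that 8.4.2 should say that the rule applies inside the imputation.

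3. **Other records show the cause.** SAP 8.4.1 lists the affected subjects with their discontinuation reasons, and SAP 7.1 tabulates reasons by arm. These help a reader judge, but they do not separate the two contributions to the imputed estimate.

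4. **Imputing all missing data is a conventional check on missing = not clear.** True, and legitimate under that name. It answers a different question from the one SAP 8.4.2 poses.

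**Conclusion.** The concern holds as a mismatch between the stated purpose and the written method. The second analysis is not restricted to COVID-19 missingness, so it can depart from the primary result with no COVID-19 effect, and a departure cannot be attributed to COVID-19.

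The size is about 3 to 6 points under assumed clearance of 35% v 5% and equal non-COVID missingness of 10% to 20%, and less if the 8.4 failures are held fixed. Larger shifts need a large dropout imbalance that 8.4 does not cover. A reader might also infer an inflated false-positive rate, but that too would rest on such an imbalance and on imputing subjects whom 8.4 scores as failures.

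The impact is modest: this is one of two sensitivity analyses, SAP 8.6 calls all comparisons exploratory, and no sample size was powered on this endpoint. The change is still worth making, because it is cheap and lets the check answer its own question.

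**What to change.** In SAP 8.4.2, second bullet:

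- Impute only Day 84 values that are missing because of COVID-19, meaning that the missed Day 84 visit, or the discontinuation before it, is recorded as due to COVID-19. An earlier COVID-19-affected date alone should not qualify. The date in SAP 8.4.1 is the earliest one, so it would also catch a subject who missed Visit 2 for COVID-19 and was later lost for another reason.
- Keep every other missing Day 84 value as not clear in all 100 datasets.
- State that subjects scored as failure or non-responder under SAP 8.4 keep that outcome in every dataset.
- If imputation of all missing data is also wanted, report it separately as a general missing-at-random sensitivity analysis.

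The cost is a few sentences and one condition in the imputation program. The reason for each missing Day 84 visit must be taken from the deviation log and discontinuation records. Fewer values are imputed, so the COVID-19 check no longer doubles as a general missing-data analysis.

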8.4.3. Handling of Missing Data for Treatable Wart Count Endpoints

Assessment of number of treatable warts is planned for the baseline visit, the EOT visit, follow-up visits (including EOS), and each treatment visit. Endpoints that are based on these assessments include percent reduction from baseline of treatable warts, change from baseline in treatable warts, percent reduction from baseline in total wart area, change from baseline in total wart area, and proportion of subjects exhibiting reduction of at least 1 treatable wart from baseline. No imputation will be done on missing data for these endpoints.

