In Part B, approximately 90 subjects will be enrolled and randomized to one of four treatment arms: VP-102 Regimen 1, Placebo Regimen 1, VP-102 Regimen 2, or Placebo Regimen 2, in a 3:2:3:2 ratio, respectively and stratified by gender. Regimen 1 and 2 refer to one of the skin exposure times (2-hour, 6-hour, or 24-hour) selected from Part A. Procedures for Part B will follow those in Part A with the exception of the Safety Review Panel.

4. Determination of Sample Size

No formal power calculations were performed for this study. The study will enroll approximately 18 subjects in Part A to determine the dose selection and approximately 90 subjects in Part B to evaluate wart clearance rates and support future trials.

5. Statistical Methods

The statistical analyses will be reported using summary tables, figures and listings (TFLs). Numbering for TFLs will be based on the recommended numbering convention provided by the International Conference on Harmonization. Continuous variables will be summarized with means, standard deviations, medians, minimums and maximums. Categorical variables will be summarized by counts and percent of subjects in corresponding categories. Where appropriate, 95% confidence intervals will be included. Missing values are not considered for percent calculations, unless stated otherwise. In those cases, footnotes will specify the percent basis.

Individual subject data obtained via the electronic data capture (EDC) system and from external vendors will be presented in listings and sorted by subject number and visit/visit date if appropriate. Data will be summarized in tables and/or figures by treatment group.

Treatments in Part A will be pooled with Part B where applicable. For example, if VP-102 24-hour exposure is one of the treatments selected for Part B, then the data from Group 3 (24-hour exposure) in Part A will be pooled with the 24-hour exposure data in Part B. The data from Part A will be summarized separately in a descriptive manner. Treatment comparisons will be made separately for each regimen, i.e., VP-102 Regimen 1 vs Placebo Regimen 1 and VP-102 Regimen 2 vs Placebo Regimen 2.

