9.2. Change and Percent Change in Number of Warts

Number of warts present will be recorded at each treatment visit as well as follow-up visits. For each post baseline treatment visit, the change in number of warts from baseline will be calculated. Summary statistics of number of warts will be displayed for each treatment visit. Summary statistics of change in number of warts from baseline will also be displayed. Statistical analyses on each treatment regimen will be performed. A restricted maximum likelihood-based repeated-measures approach, using a Mixed effect Model Repeat Measurement (MMRM) will be used. The MMRM model will include the fixed, categorical effects of treatment, gender, visit, and treatment-by-visit interaction as well as the continuous, fixed covariate of baseline wart count. An unstructured (co)variance structure shared across treatment groups will be used to model the within-subject errors. If convergence is not met, then the Akaike's Information Criteria will be used to select the best covariance structure to model the data. The Kenward-Roger approximation will be used to estimate denominator degrees of freedom and adjust standard errors.

Percent change of warts will be calculated at each post baseline visit. Percent change will be calculated using the following formula (in formula below, warts refers to treatable warts):

$$\text{Percent (\%) Change} = \frac{(\text{Warts}_{\text{Visit}} - \text{Warts}_{\text{Baseline}}) / \text{Warts}_{\text{Baseline}}}{1} * 100$$

Analysis of percent change in number of warts will be carried out in the same manner as change in number of warts.

An additional analysis will be carried out by visit to report the number and percent of subjects who had a reduction of one or more treatable warts from baseline. The proportion of subjects with 90% and 75% clearance of warts will also be analyzed using a CMH test.

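### Complete clearance counts missing as failure on all ITT subjects, but 90%, 75% and at-least-one-wart response use observed subjects only, so the rates rest on different denominators

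*SAP*

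**What the plan says.** The SAP makes ITT the primary efficacy population (Section 8) and then sets several rules for response endpoints that all derive from wart counts.

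- **Complete clearance (SAP 8.4.2).** A subject without an assessment in the window "will be considered to have not achieved complete clearance of all treatable warts at that visit". The subject stays in the denominator at every scheduled visit.
- **Reduction of at least one wart (SAP 8.4.3).** This endpoint is listed by name, and the rule for the list is "No imputation will be done on missing data for these endpoints".
- **90% and 75% clearance.** SAP 8.4.3 does not name them. SAP 9.2 gives the test only: "The proportion of subjects with 90% and 75% clearance of warts will also be analyzed using a CMH test". They fall back on the SAP 8.4 default, "Unless described otherwise in subsequent sections, analyses will be carried out with the data available using no imputation for missing data", and on the denominator rule in SAP Section 5, "Missing values are not considered for percent calculations, unless stated otherwise".
- **Failure rules (SAP 8.4).** For a withdrawal requested because of study-related adverse events or spreading disease, "data will be collected and analyzed as a treatment failure and not replaced". A second sentence reads "If a subject discontinues use of study drug but remains in the study, the subject will be analyzed as a non-responder as well". Neither is limited to complete clearance.

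Protocol 12.7 sets missing as failure for the primary endpoint. It leaves the other endpoints, and the use of treatment failure in the analysis, to the SAP.

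**The concern.** A subject with no Day 84 count is a failure in the complete-clearance table and is absent from the denominator of the 90%, 75% and at-least-one-wart tables. Read side by side, these tables look like one graded response scale, but they describe different sets of subjects.

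This matters because Part B is meant to identify the regimen with the better risk:benefit profile, and the trial is meant to supply clearance rates for later trials. Cross-regimen comparison has no formal test (Protocol 12.3), so readers will rely on the displayed percentages. SAP 8.4.1 expects missed assessments because of COVID-19, yet both sensitivity analyses in SAP 8.4.2 concern complete clearance at Day 84 only.

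The second problem is that the SAP 8.4 failure and non-responder rules meet the no-imputation rule without any order of precedence. Two programmers could follow the SAP and produce different tables.

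**Working it through.** The documents state no response rate, dropout rate or power, so there is no plan figure to reproduce. All responder and missing counts below are assumptions.

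**Arm sizes.** Part B: 90 × 3/10 = 27 VP-102 and 90 × 2/10 = 18 placebo per regimen. Part A adds 5 and 1 for a selected regimen (5:1 in groups of six). Pooled: 32 and 19.

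**Factor.** With n subjects, m missing and x responders, the observed-case rate is x/(n − m) and the missing-as-non-response rate is x/n. Their ratio is 1/(1 − m/n):

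| Missing | 5% | 10% | 15% | 20% | 25% | 30% |
|---|---|---|---|---|---|---|
| Ratio | 1.05 | 1.11 | 1.18 | 1.25 | 1.33 | 1.43 |

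With no missing data the ratio is 1.

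**Denominator artefact.** Take 32 subjects, 5 missing, and 11 responders at 90%, all of them fully clear. Complete clearance is 11/32 = 34.4%; 90% clearance is 11/27 = 40.7%. The 6.4-point gap contains no difference in response.

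**Similar missingness in both arms.** Assume 5/32 and 3/19 missing, with 13 v 1 responders at 90%, 16 v 2 at 75% and 22 v 7 at one wart or more.

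| Endpoint | Observed case | Difference | Missing = non-response | Difference |
|---|---|---|---|---|
| 90% | 13/27 = 48.1% v 1/16 = 6.2% | 41.9 | 13/32 = 40.6% v 1/19 = 5.3% | 35.4 |
| 75% | 16/27 = 59.3% v 2/16 = 12.5% | 46.8 | 16/32 = 50.0% v 2/19 = 10.5% | 39.5 |
| ≥1 wart | 22/27 = 81.5% v 7/16 = 43.8% | 37.7 | 22/32 = 68.8% v 7/19 = 36.8% | 31.9 |

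**Direction of the treatment difference.** Keep the responders and change the missing counts. The shift is observed-case difference minus non-response difference, in points:

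| Missing VP-102, placebo | 90% | 75% | ≥1 wart |
|---|---|---|---|
| 8/32, 2/19 | +12.9 | +15.4 | +18.6 |
| 3/32, 6/19 | +1.8 | +0.3 | −9.9 |

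**Against the true rate.** Let 15% be missing and the observed rate be 50%. The full-sample rate is 0.85 × 50% + 0.15 × p, where p is the response rate among the missing: 42.5% for p = 0, 45.5% for p = 20%, 50% for p = 50% and 54.5% for p = 80%. The observed-case figure is too high in the first two cases, right in the third and too low in the fourth.

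**Order of the rates.** Every clear subject is also a 90% responder, so x90 ≥ xclear; and n − m ≤ n. Hence x90/(n − m) ≥ xclear/n always. Enumeration for n = 32 and n = 19 found no reversal.

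**The SAP 8.4 ambiguity.** For 13 responders of 32 with 5 missing, the 90% rate is 13/27 = 48.1% if none of the missing is kept as a failure, 13/29.5 = 44.1% if half are, and 13/32 = 40.6% if all are.

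**Visits 2–4.** SAP Section 8 counts a treatment visit only if drug was applied, and SAP 8.4 says clear subjects attend without being treated. Suppose all 32 attend and 10 are 75% responders, 4 of them clear and untreated. The rate is 10/32 = 31.3%. Read literally, SAP Section 8 removes the 4, giving 6/28 = 21.4%. Adding missing-as-non-response without amending that rule gives 6/32 = 18.8%. The remedy must deal with both rules together.

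**The case against.** The strongest reply is that 8.4 and 8.4.3 can be read together: 8.4 classifies withdrawals for adverse events or spreading disease as failures, and 8.4.3 governs whatever is still missing. On that reading most of the clinically informative dropouts stay in the denominator. The reading is consistent, but the SAP does not state it. A reader might infer that these subjects certainly disappear from the partial-response tables; the documents leave that open.

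A reader might also infer that the partial-response rates are biased upward, or biased in favour of VP-102. The text does not support either. Observed-case rates are higher than non-response rates by construction. They are unbiased if data are missing completely at random, which missed COVID-19 visits might approximate, and the treatment difference can shrink. Nor does the ordering of complete, 90%, 75% and at-least-one-wart response break down. Only the denominators differ.

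It is also fair that the quoted 8.4.3 sentence does not name 90% or 75% clearance, and that SAP Section 5 requires a footnote where the percent basis departs from its default. Such a footnote would disclose the mismatch without removing it.

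Finally, the consequence is limited. The primary endpoint already has a clear rule and two sensitivity analyses, all comparisons are exploratory (SAP 8.6), the at-least-one-wart endpoint has only counts and percentages planned, and Protocol 12.7 is not breached on the choice of method. All of that stands, and it bounds the importance of the point. The mismatch and the missing order of precedence remain.

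**Conclusion.** The point holds as an inconsistency of denominators and an unresolved rule. Relative to the primary endpoint's own rule, partial-response rates are higher by 1/(1 − missing fraction), or 11% to 25% in relative terms if 10% to 20% are missing. In the assumed example with about 16% missing in both arms, treatment differences change by 5.8 to 7.3 points. With other missing patterns the change ran from −9.9 to +18.6 points.

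These sizes rest on assumed missing and responder counts; only the arm sizes follow from the documents. The comparison is with missing as non-response, so it does not establish bias against the true rate. The primary endpoint is unaffected. The point concerns secondary (90%, 75%) and exploratory (at least one wart) endpoints and is worth settling before database lock.

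**What to change.** Amend the SAP before lock:

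1. In 8.4.3 and 9.2, name 90% clearance, 75% clearance and reduction of at least one wart. Score missing as non-response at each visit on the full ITT denominator, as for complete clearance, and report the observed-case version as supportive.
2. State that the 8.4 treatment-failure and non-responder rules apply to these three endpoints, including where a count was observed after study drug was stopped.
3. In Section 8, amend the treatment-given condition so that a subject who attends Visit 2, 3 or 4 and is untreated because clear keeps the observed count and is not treated as missing. Without this, item 1 would turn cleared subjects into failures.
4. Leave the change and percent-change endpoints analysed by MMRM without imputation.

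The cost is a paragraph of SAP text and a few lines of code. The reported secondary and exploratory responder rates will be somewhat lower wherever data are missing, and missingness unrelated to response, such as a visit missed because of COVID-19, will be scored conservatively. The supportive observed-case table shows how much that matters.
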